Appendix 2. Clinical Laboratory Tests

Clinical Laboratory Tests

Hematology^a

Hemoglobin
 Hematocrit
 Erythrocyte count (RBC)
 Mean cell volume
 Mean cell hemoglobin concentration
 Leukocytes (WBC)
 Neutrophils, segmented
 Lymphocytes
 Monocytes
 Eosinophils
 Basophils
 Platelets

Clinical Chemistry^a

Serum Concentrations of:

Sodium
 Potassium
 Total bilirubin
 Direct bilirubin
 Alkaline phosphatase
 Alanine aminotransferase (ALT)
 Aspartate aminotransferase (AST)
 Blood urea nitrogen (BUN)
 Creatinine
 Uric acid
 Calcium
 Glucose, nonfasting
 Albumin
 Cholesterol
 Creatine kinase (CK)

Pregnancy Test (females only)^{b,c}

Lumbar Puncture (screening or optional)^{a, d}

Solanezumab
 A β proteins
 Tau proteins

Abbreviations: A β = amyloid- β peptide; LP = lumbar puncture; PET = positron emissions tomography; RBC = red blood cells; WBC = white blood cells.

^a Assayed by Lilly-designated (central) laboratory.

^b Assayed by local or investigator-designated laboratory.

^c Female patients of childbearing potential must test negative on a serum pregnancy test at screening and must test negative on a urine pregnancy test on the day of any PET scan, prior to the administration of radiopharmaceutical agent.

^d Patients who undergo LP will have coagulation panel (prothrombin time [PT]/International Normalized Ratio [INR] and partial thromboplastin time [PTT]) and platelet count) obtained from a local laboratory up to 4 weeks before each LP.

Appendix 3. Hepatic Monitoring Tests for Treatment-Emergent Abnormality

Selected tests may be obtained in the event of a treatment-emergent hepatic abnormality and may be required in follow-up with patients in consultation with the Lilly, or its designee, clinical research physician.

Hepatic Monitoring Tests

Hepatic Hematology^a

Hemoglobin
Hematocrit
RBC
WBC
Neutrophils, segmented
Lymphocytes
Monocytes
Eosinophils
Basophils
Platelets

Hepatic Chemistry^a

Total bilirubin
Direct bilirubin
Alkaline phosphatase
ALT
AST
GGT
CPK

Haptoglobin^a

Hepatic Coagulation^a

Prothrombin Time
Prothrombin Time, INR

Hepatic Serologies^{a,b}

Hepatitis A antibody, total
Hepatitis A antibody, IgM
Hepatitis B surface antigen
Hepatitis B surface antibody
Hepatitis B Core antibody
Hepatitis C antibody
Hepatitis E antibody, IgG
Hepatitis E antibody, IgM

Anti-nuclear antibody^a

Alkaline Phosphatase Isoenzymes^a

Anti-smooth muscle antibody (or anti-actin antibody)^a

Abbreviations: ALT = alanine aminotransferase; AST = aspartate aminotransferase; CPK = creatinine phosphokinase; GGT = gamma-glutamyl transferase; Ig = immunoglobulin; INR = international normalized ratio; RBC = red blood cells; WBC = white blood cells.

^a Assayed by Lilly-designated or local laboratory.

^b Reflex/confirmation dependent on regulatory requirements and/or testing availability.

Appendix 4. Summary of Radiation Dose

Patients who undergo florbetapir PET scans to determine eligibility for the study will be exposed to radiation during the PET scan. Details on the amount of exposure estimated to occur on each PET imaging occasion, in each year of the study, and cumulatively, are provided in [Table LZBE.2](#) below.

Table LZBE.2. Effective Radiation Dose (mSv) from Florbetapir PET Scans

| | Effective Dose (mSv) per Scan ^a | Number of Scans in First Year | Effective Dose (mSv) for Scans in First Year | Number of Scans in Second Year ^b | Effective Dose (mSv) for Scans in Second Year ^b | Total Effective Dose (mSv) |
|---|--|-------------------------------|--|---|--|----------------------------|
| Florbetapir F 18 (amyloid) Scan (10 mCi iv) | 7.43 | 1 | 7.43 | 1 | 7.43 | 14.86 |

Abbreviations: CT = computed tomography; iv = intravenous infusion; PET = positron emission tomography.

^a Dose shown includes radiation exposure from the radiotracer and also assumes a non-clinical CT scan is obtained (estimated at 0.4 mSv) as part of the PET scan attenuation correction process when the scan is done on a PET/CT scanner. A clinical CT scan is not needed during the PET scan session and because it would add additional radiation exposure is not recommended.

^b Second florbetapir scan done at end of second year or in the event of early discontinuation.

Source: Florbetapir F18 Injection (Amyvid™) Package Insert, 2016.

Leo Document ID = 43ed0b34-a8cf-4fbd-b58b-a82339d146d4

Approver: PPD
Approval Date & Time: 28-Mar-2016 20:03:21 GMT
Signature meaning: Approved

Approver: PPD
Approval Date & Time: 28-Mar-2016 20:59:47 GMT
Signature meaning: Approved

6.7.	.5. Magnetic Resonance Imaging Data	13
6.7.	.6. Suicidal Ideation or Behavior	13
6.8.	Interim Analyses and Data Monitoring	13
7. Re	eferences	14

Table of Contents

Table	Page
Table LZBE.4.1. Objectives and Endpoints	5
Table LZBE.6.1. Analysis Populations for Study H8A-MC-LZBE	10
Table LZBE.6.2. Study Measures Summarized for Each Analysis Population	10

3. Revision History

SAP Version 1 will be approved prior to the first production data transfer.

4. Study Objectives

Table LZBE.4.1 shows the objectives and endpoints of the study.

Table LZBE.4.1. Objectives and Endpoints

Objectives	Endpoints
Primary To assess the hypothesis that solanezumab 400 mg Q4W will slow the clinical progression of prodromal AD over 24 months compared to placebo	ADAS-Cog ₁₄ : change from baseline over 24 months
Secondary To assess the effect of solanezumab vs placebo on the clinical progression of prodromal AD over 24 months	Changes from baseline to 24 months on ADCS-MCI-ADL, MMSE, MoCA, FAQ, NPI, CDR-SB, RBANS, and FCSRT
To assess the effect of solanezumab vs placebo on quality of life and health outcomes in prodromal AD over 24 months	Changes from baseline to 24 months on RUD-Lite, EQ-5D, QoL-AD
To assess the effect of solanezumab vs placebo on biomarkers in prodromal AD over 24 months	Changes from baseline to 24 months in florbetapir PET or CSF Aβ/tau, vMRI, plasma Aβ, plasma solanezumab, sample storage for biomarkers (where permitted); includes CSF collected via optional addendum
To assess the hypothesis that solanezumab will slow the accumulation of tau pathology over 12 and 24 months compared to placebo	Changes from baseline in neocortical tau deposits (collected in a subset of subjects using ¹⁸ F-AV-1451 PET as part of an addendum) over 12 and 24 months
To assess the hypothesis that change from baseline in accumulation of tau pathology over 12 and 24 months is associated with changes from baseline in cognition	Changes from baseline in neocortical tau deposits (collected in a subset of subjects using ¹⁸ F-AV-1451 PET as part of an addendum) and ADAS-Cog ₁₄ , over 12 and 24 months
To assess the hypothesis that change from baseline in accumulation of tau pathology over 24 months is associated with changes from baseline in function	Changes from baseline in neocortical tau deposits (collected in a subset of subjects using ¹⁸ F-AV-1451 PET as part of an addendum) and ADCS-MCI-ADL over 24 months
To assess the effect of pharmacogenomic factors on clinical and functional progression with solanezumab vs placebo in prodromal AD over 24 months	Changes from baseline in pharmacogenomics markers (where permitted) and clinical and functional scales

Objectives and Endpoints

Objectives and Endpoints		
Objectives	Endpoints	
Exploratory		
To generate additional data for validation of the	Changes from baseline in components of the MMSE,	
PACC score, a composite endpoint being used in	RBANS, and FCSRT over 24 months	
another Lilly study		
To compare MMSE and MoCA scales	Changes from baseline in MMSE and MoCA over	
	24 months	
To assess time to significant progression	Time to progression to CDR-SB score of 1.0, and significant	
	change on other cognitive and functional measures	

Abbreviations: $A\beta$ = amyloid- β peptide; AD = Alzheimer's disease; ADAS- COG_{14} = 14-item Alzheimer's Disease Assessment Scale-Cognitive subscale; ADCS-MCI-ADL = Alzheimer's Disease Cooperative Study-Mild Cognitive Impairment-Activities of Daily Living Inventory; CDR-SB = Clinical Dementia Rating-Sum of Boxes; CSF = cerebrospinal fluid; EQ-D = EuroQol 5-Dimensional Health-Related Quality of Life Scale; E Functional Activities Questionnaire; E Free and Cued Selective Reminding Test; E MMSE = Mini-Mental State Examination; E MoCA = Montreal Cognitive Assessment; E NPI = Neuropsychiatric Inventory; E Preclinical Alzheimer's Cognitive Composite; E PeT = positron emission tomography; E Q4W = every 4 weeks; E QoL-E Quality of Life in Alzheimer's Disease (scale); E RBANS = Repeatable Battery for the Assessment of Neuropsychological Status; E RUD-Lite = Resource Utilization in Dementia-Lite; E vMRI = volumetric magnetic resonance imaging.

5. Study Design

5.1. Summary of Study Design

Study H8A-MC-LZBE (LZBE) is a multicenter, randomized, double-blind, parallel, placebo-controlled Phase 3 trial comparing solanezumab with placebo for 24 months in approximately 2450 subjects with prodromal Alzheimer's disease (AD). Subjects who meet entry criteria will be randomized in a 1:1 ratio to receive an infusion of solanezumab 400 mg or placebo once every 4 weeks. Subjects will be randomized by site and by use of florbetapir positron emission tomography (PET) scanning or cerebrospinal fluid (CSF) for study eligibility. The primary hypothesis being tested in Study LZBE is that solanezumab will slow the clinical progression of AD as compared with placebo in subjects with prodromal AD.

In addition, participants in the ¹⁸F-AV-1451 tau imaging addendum will be included in an interim analysis designed to assess the relationship between ¹⁸F-AV-1451 tau PET and solanezumab treatment.

Three months after the end of the double-blind treatment period (or 4 months after the last dose in case of early discontinuation), subjects will come to a follow-up visit for biomarker and safety assessments.

5.2. Determination of Sample Size

Power and sample size calculations have been based on the analysis of the primary objective using an effect size calculation of treatment difference at the end of the study.

To calculate power, an expected decline in 14-item Alzheimer's Disease Assessment Scale-Cognitive subscale (ADAS-Cog₁₄) at 2 years of 4.41 points for placebo-treated subjects and 3.21 points for solanezumab-treated subjects was used, with a common standard deviation of 8 (Doraiswamy et al. 2014). This is equivalent to a difference of 1.2 points over 2 years, with an effect size = 0.15. Based on these assumptions and a 25% discontinuation rate, 1225 randomized subjects per arm (919 completers per arm) or 2450 total randomized subjects will have approximately 89% power to detect a significant treatment difference at 2 years using a 2-sided significance level of 0.05.

Subjects who are randomized but not administered treatment may be replaced to ensure that enough subjects complete the study.

5.3. Method of Assignment to Treatment

Subjects who meet all criteria for enrollment will be randomized to double-blind treatment at Visit 2. Assignment to treatment groups will be determined by a computer-generated random sequence using an interactive web-response system (IWRS). The IWRS will be used to assign a vial containing double-blind investigational product to each subject. Site personnel will confirm the correct vial has been located by entering a confirmation number found on the vial into the IWRS.

To achieve between-group comparability, the randomization will be stratified by site and by use of florbetapir PET scanning or CSF for study eligibility.

6. A Priori Statistical Methods

6.1. General Considerations

Statistical analysis of this study will be the responsibility of Eli Lilly and Company (hereafter Lilly).

On 10 January 2017, approximately 6 months after the first subject entered the LZBE study, the study was discontinued due to sponsor decision. After careful review of additional data analyses from the solanezumab Phase 3 EXPEDITION3 (H8A-MC-LZAX) study in subjects with mild dementia due to AD, Lilly did not find sufficient scientific evidence that solanezumab would likely demonstrate a meaningful benefit to subjects with prodromal AD as defined by the LZBE study protocol. The study was not stopped for safety reasons. Based on EXPEDITION3 results, there were no new safety signals identified.

The 26 randomized subjects in the study are to be discontinued from the double-blind treatment period at the early discontinuation visit and are requested to return to the follow-up visit (Visit 301) 4 months after the last dose according to the protocol. The study DBL will happen at the end of the trial after the last subject has completed the follow-up visit. A synopsis report with attachments will summarize the study results for the early discontinued study and this statistical analysis plan will pre-specify analyses for the study synopsis.

In general, no analyses will be conducted to address any primary, secondary, or exploratory efficacy objectives because sufficient data will not be available for reliable efficacy evaluation in this early discontinued study. Safety data will be listed or summarized. No statistical comparison of treatment effect will be conducted.

All analyses will follow the intent-to-treat (ITT) principle unless otherwise specified. An ITT analysis is an analysis of data by the groups to which subjects are assigned by random allocation, even if the subjectdoes not take the assigned treatment, does not receive the correct treatment, or otherwise does not follow the protocol. When change from baseline is assessed, subjects will be included in the analysis only if both a baseline and a postbaseline measure are available. Unless otherwise defined, a baseline measure is the last non-missing observation collected prior to the first infusion of study medication. Endpoint is the last non-missing postbaseline measurement.

6.2. Handling of Dropouts or Missing Data

6.2.1. Handling of Missing Items for Scales

If any of the individual items for the ADAS-Cog or Alzheimer's Disease Cooperative Study-Mild Cognitive Impairment-Activities of Daily Living Inventory (ADCS-MCI-ADL) are missing or unknown, every effort will be made to obtain the score for the missing item or items.

For ADAS-Cog₁₄, if <30% (4 or fewer of a total of 14) of the items are missing, the total score (maximum = 90) will be imputed as follows: The total from remaining items will be multiplied by a factor that includes the maximum score for the missing items. For example, if the first item, "Word-Recall Task," which ranges from a score of 0 through 10 (maximum = 10), is missing,

and the second item "Commands," which ranges from a score of 0 to 5 (maximum = 5), is missing, then the multiplication factor = 90/(90 - [10 + 5]) = 90/75 = 1.2. Thus, the total score for this example will be the sum of the remaining 12 items multiplied by 1.2. The imputed number will be rounded up to the nearest integer. If more than 4 items are missing, the total score for ADAS-Cog₁₄ at that visit will be considered missing.

For the ADCS-MCI-ADL, if <30% of the items are missing, the total score will be imputed. The sum of the nonmissing items will be prorated to the sum of total items. The imputed number will be rounded up to the nearest integer. If the nearest integer is greater than the maximum possible score, the imputed score will be equal to the maximum score. If >30% of the items are missing, the total score for ADCS-MCI-ADL at that visit will be considered missing.

The same imputation technique will be applied to the Clinical Dementia Rating-Sum of Boxes (CDR-SB). If only 1 box (of 6) of the CDR is missing, the sum of the boxes will be imputed by prorating the sum from the other 5 boxes. If the score from more than 1 box is not available, the CDR-SB at that visit will be considered missing.

For all other scales, if any item is missing, any total or sum involving that item will be considered missing.

6.3. Analysis Populations

Table LZBE.6.1 below defines each of the analysis populations used in this study. Table LZBE.6.2 lists the study measures that will be summarized and/or analyzed in each population.

Table LZBE.6.1. Analysis Populations for Study H8A-MC-LZBE

Population Name	Description of Population
All Subjects Entered	All subjects who signed informed consent.
ITT Population	All randomized subjects.
Safety Population	All randomized subjects with at least 1 complete or partial infusion of study medication.

Abbreviation: ITT = intent-to treat.

Table LZBE.6.2. Study Measures Summarized for Each Analysis Population

Population Name	Variables Assessed
ITT Population	Tables and Listings of the following: subject disposition, subject characteristics, and concomitant medications
Safety Population	Tables and Listings of the following: adverse events, laboratory results, vital signs, MRI safety data, and suicidal ideation or behavior

Abbreviations: ITT = intent-to treat; MRI = magnetic resonance imaging.

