Analysis of Safety Data: Safety will be assessed by summarizing adverse events, laboratory analytes, vital signs, weight, electrocardiograms, magnetic resonance imaging, and Columbia Suicide Severity Rating Scale (C-SSRS) results. Comparisons will be made between the treatment groups.

2. Schedule of Activities

| Study Period | I | II | | | | | | | |
|--|-----------|-----------------|----|----|----|----|----|----|----|
| | Screening | Double Blind | | | | | | | |
| Suggested Interval | 6 weeks | 4 weeks | | | | | | | |
| Interval Allowed (days) | -0 to -56 | 21 – 35 | | | | | | | |
| Visit | V1 | V2 ^a | V3 | V4 | V5 | V6 | V7 | V8 | V9 |
| End of Week Relative to Study Medication Start ^b | -4 | 0 | 4 | 8 | 12 | 16 | 20 | 24 | 28 |
| Entry/Administrative Procedures | | | | | | | | | |
| Informed consent | X | | | | | | | | |
| Patient number assigned via IWRS | X | | | | | | | | |
| Inclusion/exclusion review | X | X | | | | | | | |
| Modified Hachinski Ischemia Scale | X | | | | | | | | |
| Physical/neurological exam | X | | | | | | | | |
| Medical history | X | | | | | | | | |
| Demographics, height, and habits | X | | | | | | | | |
| Florbetapir PET scan or lumbar puncture for study entry ^c | X | | | | | | | | |
| Randomization | | X | | | | | | | |
| Previous/concomitant medications | X | X | X | X | X | X | X | X | X |
| Preexisting conditions/adverse events | X | X | X | X | X | X | X | X | X |
| Study drug administered ^b | | X | X | X | X | X | X | X | X |
| Efficacy and Health Outcomes Assessments | | | | | | | | | |
| FCSRT | X | | | | | | | | |
| MoCA | X | | | | | | | | |
| FAQ | X | | | | | | | X | |
| ADAS-Cog ₁₄ | | X | | | X | | | X | |
| ADCS-MCI-ADL | | X | | | X | | | X | |
| CDR-SB | | X | | | | | | | |
| RBANS | | X | | | | | | | |
| MMSE | | X | | | | | | X | |
| NPI | | X | | | | | | X | |
| RUD-Lite | | X | | | | | | X | |
| EQ-5D | | X | | | | | | X | |
| QoL-AD | | X | | | | | | X | |

| Study Period | I | II | | | | | | | |
|--|--------------------|-----------------|----|----|----|----|----|----|----|
| | Screening | Double Blind | | | | | | | |
| | Suggested Interval | 4 weeks | | | | | | | |
| Interval Allowed (days) | -0 to -56 | 21 – 35 | | | | | | | |
| Visit | V1 | V2 ^a | V3 | V4 | V5 | V6 | V7 | V8 | V9 |
| End of Week Relative to Study Medication Start ^b | -4 | 0 | 4 | 8 | 12 | 16 | 20 | 24 | 28 |
| Blood Sampling | | | | | | | | | |
| Clinical chemistry, hematology | X | | | | | | | X | |

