9.3. Other Safety Assessments

9.3.1. Physical Examinations and Neurologic Examination

Physical and neurological examinations will be conducted as specified in the Schedule of Activities (Section 2) and as clinically indicated.

Physical examinations will include assessment of general appearance, skin, head and neck, lymph nodes, thyroid, abdomen (bowel sounds and liver and spleen palpation), back (costovertebral angle tenderness), and musculoskeletal, cardiovascular, and respiratory systems. Neurological examinations will include assessment of cranial nerves, motor and sensory systems, muscle stretch reflexes, balance and coordination, and gait. The physical and neurological

examination will be performed by a physician, nurse practitioner, or physician's assistant (for Japan, physician only).

Body weight and height will be recorded according to the Schedule of Activities (Section 2).

If a clinically meaningful change in an MRI is noted during the study, an additional full neurological exam will be performed as soon as possible, along with any other medical follow-up deemed necessary by the investigator.

Any clinically significant change from baseline on follow-up physical and neurological examinations should be reported to Lilly or its designee as an AE via CRF.

9.3.2. *Electrocardiograms*

For each patient, ECGs should be collected according to the Schedule of Activities (Section 2). Electrocardiograms should be recorded according to the study-specific recommendations included in the manual of operations for the study.

Electrocardiograms will initially be interpreted by a qualified physician (the investigator or qualified designee) at the site as soon after the time of ECG collection as possible, and ideally while the patient is still present, to determine whether the subject meets entry criteria and for immediate patient management, should any clinically relevant findings be identified.

All ECGs will be electronically transmitted to a designated central ECG laboratory. A cardiologist at the central ECG laboratory will then conduct a full overread. A report based on data from this overread will be issued to the investigative site. When there are differences in ECG interpretation between the local and central readings, the locally read interpretation will be used for study entry and immediate patient management, and the centrally read interpretation will be used for data analysis and report writing purposes.

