10.5. Safety Analyses

Safety will be assessed by summarizing and analyzing AEs, laboratory analytes, vital signs, weight/height measurements, MRI scans, ECGs, and immunogenicity measures during the treatment period.

Safety analyses for the treatment period will include comparisons between solanezumab and placebo. All hypotheses will be tested at a 2-sided 0.05 significance level. No adjustments for multiple comparisons will be made.

For analysis comparing proportion of treatment-emergent abnormalities between treatment groups for laboratory analytes, vital signs, weight, MRI scans, and ECGs, only patients who have both a baseline observation and a postbaseline observation will be included in the analysis for each analyte or parameter, respectively.

Suicide-related thoughts and behaviors, based on the C-SSRS, will be listed by patient and visit. Only patients that show suicidal ideation/behavior will be displayed (that is, if a patient answers are all “no” for the C-SSRS, then that patient will not be displayed). However, if a patient reported any ideation or behavior at any time point, then all their ideation and behavior will be displayed, even if not positive.

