6.7.3. Clinical Laboratory Evaluation

Laboratory measurements for clinical chemistry and hematology panels will be summarized using continuous data (change from baseline) and categorical or ordinal data (proportion of treatment-emergent abnormalities).

Summaries and analyses of continuous lab data (change from baseline) will be performed using International System of Units (SI units). If there are multiple records of laboratory measurements at baseline or postbaseline visit, the last record for each time period will be used.

The proportion of subjects with treatment-emergent high or treatment-emergent low, or treatment-emergent abnormal laboratory values at any postbaseline visit will be summarized by treatment and overall. Treatment-emergent high or low laboratory abnormality will be based on SI unit. Planned and unplanned measurements will be included. A treatment-emergent high value is defined as a change from a low value or normal value at all baseline visits to a value greater than the high limit at any time after baseline. A treatment-emergent low value is defined as a change from a high value or normal value at all baseline visits to a value less than the low limit at any time after baseline. A treatment-emergent abnormal value (only applies to categorical results) is defined as a change from normal at all baseline visits to abnormal at any time after baseline.

For each laboratory analyte, only subjects who were low or normal at baseline and have at least one postbaseline will be included in the denominator when computing the proportion of subjects with treatment-emergent high values. Similarly, only subjects who were high or normal at baseline and have at least one postbaseline will be included in the denominator when computing the proportion of subjects with treatment-emergent low values.

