6.7.4. Vital Signs and Other Physical Findings

Summary statistics will be presented for observed values at baseline and for change from baseline results at each scheduled postbaseline visit. Systolic and diastolic blood pressure and pulse (collected in sitting position), temperature, and weight by treatment group for all subjects in the safety population will be summarized.

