6.7.5. Magnetic Resonance Imaging Data

Magnetic resonance imaging (MRI) is scheduled to be obtained at screening (Visit 1), 52 weeks (Visit 15), 104 weeks (Visit 28), and early discontinuation visit (ED). Due to early discontinuation of the study, MRI data will only be available at screening and ED. Frequencies and percentages of the following parameters of amyloid-related imaging abnormality (ARIA) edema (ARIA-E, also known as vasogenic edema) and hemorrhage (ARIA-H, also known as microhemorrhage), will be summarized.

ARIA-H

- Number of ARIA-H (1, 2 to 4, 5 to 10, >10, no presence, or nonevaluable) at screening and ED
- Shift from screening to early discontinuation

• ARIA-E

- Severity (mild, moderate, severe, questionable, nonevaluable, or no presence) at screening and ED.
- Change (unchanged in size, increased in size, decreased in size or complete resolution) from screening to ED.

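### Does the shortened SAP need ECG and immunogenicity outputs, or a stated reason for leaving them out?

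*SAP*

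**What the plan says.** Protocol 10.5 commits to summarizing and analyzing adverse events, laboratory analytes, vital signs, "weight/height measurements, MRI scans, ECGs, and immunogenicity measures during the treatment period". The protocol synopsis has a similar list, "summarizing adverse events, laboratory analytes, vital signs, weight, electrocardiograms, magnetic resonance imaging" and the C-SSRS; it includes ECG but not immunogenicity. On ECGs, Protocol 9.3.2 says that where local and central readings differ, "the centrally read interpretation will be used for data analysis and report writing purposes".

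The SAP is a reduced plan for a synopsis report on a terminated study. Section 6.1 drops the efficacy analyses for lack of data, rules out any statistical comparison of treatment effect, and says of safety only that "Safety data will be listed or summarized". For the safety population, Table LZBE.6.2 provides "Tables and Listings of the following: adverse events, laboratory results, vital signs, MRI safety data, and suicidal ideation or behavior".

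The detailed sections do not widen that list to ECG or antibodies. Section 6.7.3 begins "Laboratory measurements for clinical chemistry and hematology panels will be summarized", and 6.7.4 covers "Systolic and diastolic blood pressure and pulse (collected in sitting position), temperature, and weight by treatment group". Section 6.7.5 keeps MRI while noting: "Due to early discontinuation of the study, MRI data will only be available at screening and ED".

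**The concern.** The protocol promises two safety summaries that the SAP does not specify. The SAP explains its other cuts: insufficient data for efficacy, and early discontinuation for the interim analysis and the data monitoring committee meeting. It explains nothing about ECG or antibodies. Sparse data does not look like the explanation either, because MRI is kept although it exists only at screening and early discontinuation.

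At stake is the content of the synopsis report. An analyst who produced only the outputs named in the SAP would report no measured ECG values, no change from baseline and no anti-solanezumab results. Protocol 9.2.2.2 lists antibody-associated adverse events and cardiac arrhythmia-related events among those of special interest. Without antibody results, the first group could not be set against antibody status.

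**Working it through.** The plan states no figure on this point, so the check is mainly a comparison of texts.

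**1. Coverage of Protocol 10.5.**

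| Protocol 10.5 measure | SAP output |
|---|---|
| Adverse events | 6.7.2 |
| Laboratory analytes | 6.7.3 |
| Vital signs | 6.7.4 |
| Weight/height | weight in 6.7.4; height in 6.5 |
| MRI | 6.7.5 |
| ECG | none |
| Immunogenicity | none |

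Two of seven have no output. Against the synopsis list it is one of seven (ECG). The numbering 6.7.1 to 6.7.6 runs without a gap, so removed pages do not explain the absence.

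**2. Is Table LZBE.6.2 a closed list?** No. Exposure is planned in 6.7.1 but is not in the table. The accurate statement is that no ECG or antibody output is specified, not that none may appear.

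**3. What was scheduled** (Protocol Section 2):
- MRI: Visits 1, 15 and 28, and early discontinuation (ED).
- ECG: Visits 1, 2, 8, 15, 21 and 28, and ED.
- Anti-solanezumab serum: Visits 2, 3, 5, 8, 15, 21 and 28, and ED, where local rules allow.

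If all 26 subjects attend ED, this gives 26 × 2 = 52 pre-dose ECGs and 26 at ED. For serum it gives 26 at Visit 2 and 26 at ED, 52 in all, plus whatever was drawn at the visits in between. These are scheduled counts. The documents do not say how many ECGs were recorded, or how many samples were drawn or assayed.

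**4. What is captured elsewhere.** Under Protocol 9.3.2, a clinically significant ECG finding that results in a diagnosis after the first dose is reported as an adverse event. SAP 6.7.2 lists adverse events and counts treatment-emergent ones from the first infusion to Visit 301. Infusion reactions reported as adverse events appear in the same listing. What has no planned output is the measured ECG values and the antibody results.

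**5. What the extra output could show.** The split by arm is not given, so I assume 13 and 13 under 1:1 allocation. With 0 events among n subjects, the upper end of the exact two-sided 95% interval is 1 − 0.025^(1/n):
- n = 13: 1 − 0.025^(1/13) = 24.7%
- n = 10: 30.8%
- n = 16: 20.6%

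The last two cover an uneven 10/16 split. In each case a clean ECG or antibody table would still be compatible with a true rate of about one in five to one in three.

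**The case for a change.** The best case for a change is that the SAP departs from its own rule as well as from the protocol. Section 6.1 says without exception that safety data will be listed or summarized, and ECG and antibodies are safety data under Protocol 10.5. The remedy is cheap: a listing for 26 subjects, or a sentence giving the reason. Stating it before database lock would show that the choice was made in advance.

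The mismatch stands, and so does the loss of measured ECG values and antibody status if nobody adds a listing. Three parts of the case do not carry it further.

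- **The comparison with MRI is weak.** The schedules differ, since ECG was also due at Visits 2, 8 and 21. There is also an evident reason to keep MRI. The protocol's Introduction singles out ARIA as the most relevant treatment-emergent event from earlier Phase 3 studies, and SAP 6.7.5 summarizes exactly ARIA-E and ARIA-H. Keeping the main known imaging risk does not oblige the sponsor to keep every other measure.
- **A missing reason in the SAP is not a breach.** Protocol 10.2 asks for changes that alter no principal feature to be described and justified in the study report, which had not yet been written.
- **The rule in Section 6.1 helps the plan.** It already permits an analyst to list the centrally read ECGs, and any antibody results that exist, without amending the SAP.

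**Conclusion.** No change to the plan is needed. The SAP leaves 2 of the 7 safety measures in Protocol 10.5 without a specified output and does not say why. This is a small inconsistency in a plan cut down for a synopsis of 26 subjects. It biases no estimate and affects no test, because the SAP makes no treatment comparison, and no trial conclusion depends on it. SAP 6.1 records that the stop was not for safety and that the completed Phase 3 study in mild AD dementia raised no new safety signal. A reduced safety package is a fair choice in that setting.

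The gap is one that analysts can fill sensibly: by listing what was collected under the general rule in SAP 6.1, or by noting the omission in the report as Protocol 10.2 provides. Writing either into the SAP would add reporting detail without making the results sounder.

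This rests on three points: the ECG and antibody omissions are not a principal feature in the sense of Protocol 10.2; diagnosed ECG findings do reach the adverse event listing; and the arms are of roughly equal size. The last matters only for the illustrative limits of 20.6% to 30.8%.
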